8.2. Statistical analysis for comparison of food effect – Single dose study part

8.2.1. Endpoints/Variables

To assess the food effect in Cohort 3, the statistical analysis will be based on AUC(0-t), AUC(0-∞) and Cmax, only.

8.2.2. Summary Measure

The summary measure will be the point estimates and 90% CIs of mean differences of GSK3186899 fed – GSK3186899 fasted, based on the loge-transformed data, and after back-transformation of this estimated differences, the geometric mean ratios of (GSK3186899 fed: GSK3186899 fasted) will be presented.

8.2.3. Population of Interest

These analyses will be based on the PK population.

8.2.4. Strategy for Intercurrent (Post-Randomization) Events

In the Table 3 below, the possible intercurrent events and the rationale for relating them to treatment or otherwise is described. Once a subject discontinues from study treatment, they will proceed straight to follow up and no further data will be collected.

All subjects' data will be included in data listings irrespective of the strategies followed for the analysis.

If feasible, subjects will be replaced until the desired sample size is attained.

Table 3 Strategies for Intercurrent events

Intercurrent events	Relation to treatment and rationale	Strategy, rationale and details of action taken
Subject withdraws study consent	Not related to treatment/ Subject drops out due to logistic reasons and not due to any event related to treatment	
 - The strategy will be a While-on-Treatment strategy, where we are interested in the treatment effects prior to the withdrawal only. - Subjects' data available up to the withdrawal will be included in the food effect analyses. - If a subject withdraws consent during a period, the missing data post withdrawal will not be imputed. - The derived PK parameters for e.g., AUC, C_{max} etc. of that partially completed period will be calculated if data permits (See section 8.1.1.2 Derived Pharmacokinetic Parameters for details on derivation criteria).

Subject does not take the full treatment	
Not related to treatment/
 
The treatment will be administered as a powder dissolved in diluent. To ensure all treatment is ingested, the bottle containing the dispersion will be rinsed three times and the subject will be expected to ingest this in addition to the initial dispersion. If three rinses are not all ingested, the subject may not take the full treatment dose.
	
In the current formulation, it is hard to measure the exact proportion of dose ingested if not all rinses are taken. It is also uncertain whether the formulation could change in future development. To account for this, we propose two different strategies described below. If this intercurrent event is not observed, then both strategies will provide the same results and only the hypothetical strategy will be presented for the final analysis.
 
Primary analysis
 
 - The strategy will be a Hypothetical strategy, where we are interested in the treatment effects in a hypothetical scenario where all subjects have taken complete dose. - In this case, the data from a period in which an incomplete dose is taken would be considered as missing at random and excluded from analyses. - If the drug formulation is changed in the future studies, this estimate will provide the true relationship between the actual dose intake and its exposure under this strategy. 
Supplementary analysis
 
 - The strategy will be a Treatment policy strategy, where we are interested in the treatment effects regardless of the actual amount of dose taken. - The analysis will include PK parameters derived based on concentrations of both complete and partial doses (if data permits based on criteria described in Section 8.1.1.2) and will be analysed using the nominal or prescribed dose. - If the drug formulation remains unchanged in the future studies, this estimate will provide the true relationship between a nominal dose and its exposure under this strategy, i.e., close to a real-world situation.
Subject drops out due to	
Related to treatment/
 
If the adverse event is confirmed
	
 - The primary strategy will be a Hypothetical strategy, where we are interested in the treatment effects in a hypothetical scenario where discontinuation due to an AE would not happen.

Adverse events	to be related to study treatment	
 - The missing data after discontinuation will be assumed to be missing at random - The derived PK parameters of the last fully or partially completed period will be calculated if data permits (See section 8.1.1.2 Derived Pharmacokinetic Parameters for details on derivation criteria).
----------------	----------------------------------	---

8.2.5. Statistical Analyses / Methods

Details of the planned displays are provided in **Error! Reference source not found.**: List of Data Displays and will be based on GSK Data Standards and statistical principles. Graphical presentations will be provided if appropriate. All data will be listed.

8.2.5.1. Statistical Methodology Specification

The following statistical analyses will only be performed if sufficient data is available (i.e. if subjects have well defined plasma profiles).

Pharmacokinetic analysis will be the responsibility of the Clinical Pharmacology Modelling and Simulation Department, (CPMS) and Statistical analyses of the pharmacokinetic parameters will be the responsibility of the Biostatistics Department.

(1) Statistical analysis for comparison of food effect – Single dose study part	
Endpoint / Variables	
 • AUC (0-t) • AUC(0-∞) • Cmax
Model Specification	
 • Log_e-transformed data will be statistically analysed using a Mixed model. • The mixed model will contain 
 ○ Fixed effect: fed or fasted status, period and their interaction term (if tested as significant) ○ Random effect: subject • Only data of subjects participating in Cohort 3 will be included in this analysis, all other dose level data from Cohorts 1 and 2 will be excluded from this analysis. • The Kenward and Roger method for approximating the denominator degrees of freedom and correcting for bias in the estimated variance-covariance of the fixed effects will be used. • An unstructured type of the covariance matrices R (accounting for the within subject variability) and G (accounting for the between subject variability) will be used. • Based on the intercurrent events observed in the study, appropriate strategies from Table 3 in Section 8.2.4 will be considered for handling of missing data (if any) and interpretation of food effect analysis results. If multiple intercurrent events are observed (for e.g., if the

subject does not take the full treatment as well he withdraws study consent), then the data will be handled using more than one strategy as described in Table 3 and interpretations of the results will be made accordingly.
Model Checking & Diagnostics

For the Mixed model, model assumptions will be checked, and appropriate adjustments may be applied based on the data.Distributional assumptions underlying the model used for analysis will be examined by obtaining a normal probability plot of the residuals and a plot of the residuals versus the fitted values (i.e. checking the normality assumption and constant variance assumption of the model respectively) to gain confidence that the model assumptions are reasonable.If there are any departures from the distributional assumptions, alternative transformations, such as data squared or square root of data, will be explored.Non-parametric analyses will be conducted if the normality assumption does not hold for any of the alternative transformations.If this model fails to converge, alternative covariance structures may be considered in the following order (1) Compound Symmetry (CS) and (2) Variance Components (VC).
Model Results Presentation

Point estimates and corresponding 90% confidence intervals will be constructed for the comparisons of interest of GSK3186899 fed – GSK3186899 fasted, based on the log-transformed data.These loge-transformed results will then be exponentially back-transformed to provide point estimates and corresponding 90% confidence intervals for the geometric mean ratios (GSK3186899 fed: GSK3186899 fasted).

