### 5.6.2. Part A

**Dose escalation meeting:** The decision to proceed to the next dose level of GSK3186899 will be made at a DEC meeting based on:

- all available safety and tolerability data from a minimum of 48 hours post-dose from a minimum of 4 or more participants who have received GSK3186899 at the current dose level. Individual safety data (AEs, laboratory safety tests, telemetry, ECGs and vital signs) will be reviewed.
- all available safety and tolerability data accumulated from preceding dose levels and available PK data from current (minimum of 4 or more participants) and preceding dose levels.

**Safety review meeting:** The decision to proceed from Cohort 1 Period 4 (DL4) to Cohort 2 Period 1 (DL4), and Cohort 3 Period 1 (DLX) to Cohort 3 Period 2 (DLX-FD) will be made by the Principal Investigator and Medical Monitor based on:

- all available safety and tolerability data from a minimum of 48 hours post-dose from a minimum of 4 or more participants who have received GSK3186899 at the current dose level. Individual safety data (AEs, laboratory safety tests, telemetry, ECGs and vital signs) will be reviewed.

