## 7.3. Measures to Minimize Bias: Randomization and Blinding

### 7.3.1. Randomization

On Day 1, participants will be assigned a unique number (randomization number) in ascending numerical order. The randomization number encodes the participant's assignment to either GSK3186899 or placebo, according to the randomization schedule generated prior to the study by the Statistics Department at GSK, using validated internal software.

All participants will be centrally randomized using an Interactive Voice/Web Response System (IVRS/IWRS). Before the study is initiated, the telephone number and call-in directions for the IVRS and/or the log in information & directions for the IWRS will be provided to the site.

Study treatment will be dispensed at the study visits summarized in SoA. Each participant will be dispensed blinded study treatment, labelled with his/her unique randomization number, throughout the study. Returned study treatment should not be re-dispensed to the participants.

In Part A (Cohorts 1 and 2) and Part B (Cohorts 4-6), participants will be randomized in a 3:1 ratio to either GSK3186899 or placebo. In Part A Cohort 3, although all participants will receive GSK3186899, they will be randomized to either a fasted or fed regimen. The participants will be unblinded in this part of the study only.

Once a randomization number has been assigned to a participant, it cannot be reassigned to any other participant.

Currently, there is no indication as to the taste of GSK3186899 administered as a solution. For this reason, participants receiving GSK3186899 or placebo as a solution (in any part of this study) may also need to consume a flavoured sweet (for example a hard boiled sweet) prior to and/or immediately following dosing, provided this does not interfere with ongoing monitoring or study procedures. The need for ongoing taste masking will be determined by the DEC.

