2.3. Study Design

Overview of Study Design and Key Features		
Figure 1 Study Design (Part A)		
Screening Period (28 days prior to D1)	Treatment Period	Follow-up Period (7-14 days post last dose)
Cohort 1 N = 8 (6A:2P)	DL1 → DL2 → DL3 → DL4 → 	
Cohort 2 N = 8 (6A:2P)	DL4 → DL5 → DL6 → DL7 → 	
Cohort 3 N = 14 (14A)	DLX →  DLX-FD → 	

All doses are fasted unless otherwise specified
 
♦ = Dose escalation meeting ◆ = Safety data review meeting
		
DL = Dose level; DLX = Dose level to be determined; FD = Fed Conditions; A = Active; P = Placebo		
Figure 2 Study Design (Part B)		
Screening Period (28 days prior to D1)	Treatment Period	Follow-up Period (7-14 days post last dose)
Cohort 4 N = 8 (6A:2P)	Repeat DL1 10 days → 	
Cohort 5 N = 8 (6A:2P)	Repeat DL2 10 days → 	
Cohort 6 N = 8 (6A:2P)	Repeat DL3 10 days → 	

♦ = Dose escalation meeting
 
DL = Dose level; A = Active; P = Placebo
 
Note: DL7 was not dosed in the study due to higher than expected exposures.
		
Design Features	
This study will be a randomized, double-blind (sponsor unblinded), placebo-controlled, 2-part study of the oral administration of GSK3186899A in healthy participants.
 
Planned to include approximately 54 participants and will consist of 2 parts as below:
 
 Part A will include a single-ascending, sequential crossover design in up to 3 cohorts of participants (Cohorts 1, 2 and 3). Part A Cohorts 1-2 will comprise of a 4 period crossover which includes 4 dosing regimens under fasted conditions. Part A Cohort 3 will comprise of a 2 period crossover which includes 1 dosing regimen 	

Overview of Study Design and Key Features	
	
under fasted conditions and 1 regimen under fed conditions. The fed conditions regimen will investigate the safety, tolerability and PK of a single dose of GSK3186899 following food administration.
 
 Part B will be a twice-daily (BID) 10-day repeat dose design in up to 3 parallel cohorts of participants (Cohorts 4, 5 and 6). Part B may include drug administration after either fed or fasted conditions, this will be dependent on the interim results from Part A. If under fasted conditions, participants will be required to fast at least 2 hours before and after drug administration.

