Time & Events	
 Refer to Appendix 2: Schedule of Activities
Treatment Assignment	
 Part A consists of up to 30 participants in up to 3 cohorts (excluding possible replacements): 
 Cohort 1 and 2 will each have 6 participants in active versus 2 participants in placebo (i.e., in a 3:1 ratio)

Overview of Study Design and Key Features	
	
 ○ Cohort 3 will contain up to 14 participants in a 1:1 ratio for (fed and active) versus (fasted and active) ● Part B consists of up to 24 participants in up to 3 cohorts: 
 ○ Cohorts 4, 5 and 6 will each have 6 participants in active versus 2 participants in placebo (i.e., in a 3:1 ratio)
Interim Analysis	
No formal interim analyses (IA) are planned for this study. However, safety, tolerability, and PK data will be reviewed before each dose escalation in Part A (single dose) and Part B (repeat dose), prior to the investigation of the food effect, and between Part A and Part B.
 
An informal interim analysis for Part A will be conducted prior to initiating Part B. This analysis will support the decision to progress or not to progress to Part B.

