3.1.1.3. Safety review meetings

The decision to proceed from Cohort 1 Period 4 to Cohort 2 Period 1 and similarly progress from Cohort 3 Period 1 (DLX) to Cohort 3 Period 2 (DLX-FD) will be made by the Principal Investigator and Medical Monitor based on all available safety and tolerability data from a minimum of 48 hours post-dose from a minimum of 4 or more participants who have received GSK3186899 at the current dose level. Individual safety data (AEs, laboratory safety tests, telemetry, ECGs and vital signs) will also be reviewed. PK data will not be included in these reviews.

The study team will remain blinded until the database freeze, except for the unblinded site Pharmacist, unblinded study Pharmacokineticist and SMG Pharma Safety representative.

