10.12.6. Pharmacokinetic Tables

Pharmacokinetic: Tables					
No.	Population	IDSL / Example Shell	Title	Programming Notes	Deliverable
Pharmacokinetic Concentration Data					
4.1.	PK	PK01	Summary of GSK3186899 Plasma Pharmacokinetic Concentration-Time Data - Part A		SAC
4.2.	PK	PK01	Summary of GSK3186899 Plasma Pharmacokinetic Concentration-Time Data - Part B		SAC
Derived Pharmacokinetic Parameters					
4.3.	PK	PK06	Summary of Non-transformed Derived GSK3186899 Plasma Pharmacokinetic Parameters by Dose - Part A		SAC
4.4.	PK	PK06	Summary of Non-transformed Derived GSK3186899 Plasma Pharmacokinetic Parameters by Dose - Part B		SAC
4.5.	PK	PK05	Summary of Log _e -Transformed Derived GSK3186899 Plasma Pharmacokinetic Parameters by Dose - Part A		SAC
4.6.	PK	PK05	Summary of Log _e -Transformed Derived GSK3186899 Plasma Pharmacokinetic Parameters by Dose - Part B		SAC
4.7.	PK	Non-standard PK_T1	Statistical analysis for comparison of food effect in Part A Cohort 3		SAC
4.8.	PK	Non-standard PK_T2	Statistical Analysis of Log Transformed Plasma GSK3186899 Pharmacokinetic Parameters Assessing Dose Proportionality (Power Model) – Part A		SAC
4.9.	PK	Non-standard PK_T3	Statistical Analysis of Log Transformed Plasma GSK3186899 Pharmacokinetic Parameters Assessing Dose Proportionality (Power Model) – Part B		SAC
4.10.	PK	Non-standard PK_T4	Statistical Analysis of Log-transformed Plasma GSK3186899 Parameters Assessing Steady-State – Part B		SAC

Pharmacokinetic: Tables					
No.	Population	IDSL / Example Shell	Title	Programming Notes	Deliverable
4.11.	PK	Non-standard PK_T4	Time invariance analysis of log-transformed Plasma GSK3186899 Parameters – Part B	Update the parameters for time invariance analysis	SAC

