10.13. Appendix 13: Example Mock Shells for Data Displays

Example : PK_T1

Population : Pharmacokinetic

Table 4.7
Statistical analysis for comparison of food effect in Part A Cohort 3

Parameter (Units)	Fed		Fasted		GSK X.X mg Fed vs Fasted (Difference)	90% CI of the difference	GSK X.X mg Fed vs Fasted (Ratio)	90% CI of the Ratio
	n	LS Mean	n	LS Mean				
AUC(0-t) (μ g.h/mL)	x	xx.xx	x	xx.xx	x.xx	(x.xx, x.xx)	x.xx	(x.xx, x.xx)
Cmax (μ g/mL)	x	xx.xx	x	xx.xx	x.xx	(x.xx, x.xx)	x.xx	(x.xx, x.xx)
.....								

Log-transformed parameter is modelled with fed or fasted status and period as fixed effects and subject as a random effect. Unstructured covariance structures are considered describing within and between subject variability.

A ratio of 1 indicates same PK response is seen in both the fed and fasted subjects. A ratio > 1 indicates a higher PK response was seen in the fed subjects.

USER ID:directory/program.sas 01JAN2002 12:01

Example : PK_T2
 Population : Pharmacokinetic

Table 4.8
 Statistical Analysis of Log Transformed Plasma GSK3186899 Pharmacokinetic Parameters Assessing Dose Proportionality (Power Model) - Part A

Parameter (Units)	Slope Log Parameter vs Log Dose	90% CI of the Slope
<AUC(0-t) ($\mu\text{g.h/mL}$)>	x.xx	(x.xx, x.xx)
Cmax ($\mu\text{g/mL}$)	x.xx	(x.xx, x.xx)
.....		

A Power model is used to assess the dose proportionality.

$\text{Log}_e(\text{dose})$ and period are fitted as fixed effects and subject as a random effect. An unstructured covariance structure is considered describing between subject variability.

A slope of 1 indicates the pharmacokinetics are dose proportional. A slope greater than 1 indicates the increase in PK is greater than proportional to dose.

USER ID:directory/program.sas 01JAN2002 12:01

Example : PK_T3
 Population : Pharmacokinetic

Table 4.9
 Statistical Analysis of Log Transformed Plasma GSK3186899 Pharmacokinetic Parameters Assessing Dose Proportionality (Power Model) - Part B

Parameter (Units)	Timepoint	Slope Log Parameter vs Log Dose	90% CI of the Slope
<AUC(0-t) ($\mu\text{g.h/mL}$)>	Day 1	x.xx	(x.xx, x.xx)
	Day 10	x.xx	(x.xx, x.xx)
Cmax ($\mu\text{g/mL}$)	Day 1	x.xx	(x.xx, x.xx)
	Day 10	x.xx	(x.xx, x.xx)
.....			

A Power model is used to assess the dose proportionality.

$\text{Log}_e(\text{dose})$ is fitted as a fixed effect and subject as a random effect. An unstructured covariance structure is considered describing between subject variability.

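### Cohort 3 is described both as fixed order (fasted, then fed) and as randomised; under the fixed order the SAP food-effect model cannot estimate the final fed:fasted ratio

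*SAP*

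**What the plan says.** **Order stated as fixed**

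- Protocol 5.6.2 places a safety review before the cohort moves on; the decision to go from "Cohort 3 Period 1 (DLX) to Cohort 3 Period 2 (DLX-FD) will be made by the Principal Investigator and Medical Monitor".
- SAP 3.1.1.3 says the study will "similarly progress from Cohort 3 Period 1 (DLX) to Cohort 3 Period 2 (DLX-FD") on the same basis, and SAP 3.1 lists that review again.
- In SAP 2.3, Figure 1, a single Cohort 3 row for all 14 participants runs DLX and then DLX-FD. The legend defines the labels: "DLX = Dose level to be determined; FD = Fed Conditions". The figure note makes every dose fasted unless marked otherwise, so DLX is fasted and DLX-FD is fed.

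**Order stated as randomised**

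- Protocol 7.3.1 says of Cohort 3 that "they will be randomized to either a fasted or fed regimen".
- SAP 2.3, Treatment Assignment: "Cohort 3 will contain up to 14 participants in a 1:1 ratio for (fed and active) versus (fasted and active"). A ratio between conditions is ambiguous here, because SAP 2.3 (Dosing) gives each participant both conditions.

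**Model**

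- SAP 8.2.5.1: "Fixed effect: fed or fasted status, period and their interaction term (if tested as significant"); subject is random.
- SAP 10.13, footnote to mock Table 4.7: "Log-transformed parameter is modelled with fed or fasted status and period as fixed effects and subject as a random effect".
- Protocol 10.5.2 has fed/fasted condition and subject only, with no period term. SAP 2.1 reports no major change and lists one minor one, about Ctau. It does not mention period or the interaction.

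Neither document writes out two sequences.

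**The concern.** A two-period comparison can separate food from period only if some participants are fed in Period 1 and others in Period 2. If everyone is fasted first and fed second, the two effects cannot be told apart, and a model that asks for both has no answer for either. Taken together, Protocol 5.6.2, SAP 3.1.1.3 and SAP 8.2.5.1 ask for exactly that.

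The final geometric mean ratio and its 90% CI are at stake: SAP 10.12.6, Table 4.7, "Statistical analysis for comparison of food effect in Part A Cohort 3". By Protocol 10.2, Cohort 3 is the only cohort sized on a statistical basis, and its purpose is to determine the food effect and inform Part B dosing.

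Table 4.7 is due only at the final statistical analysis, so its failure would not by itself block the Part B fed/fasted decision. That decision draws on the interim ratio summary prepared by the pharmacokinetics function (SAP 3.1.1.2, display 18), for which no model is specified. Under a fixed order, that summary carries any period effect inside the food effect too.

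**Working it through.** **Inputs.** CVw 20% (AUC) and 30% (Cmax), n = 12 evaluable, true ratio 1, 90% two-sided interval (Protocol 10.2; SAP 8.2.5.1). The documents give no period effect, so the values used in step 5 are assumptions.

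**1. The plan's own precision figures.** Let s = √ln(1 + CVw²) and SE = s·√(2/n). Precision = exp(t(0.95, n−1)·SE) − 1.

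- AUC: s = 0.1980, SE = 0.1980 × 0.4082 = 0.0808, t(11) = 1.796, and exp(0.1452) − 1 = 15.6%. The plan states 16%.
- Cmax: s = 0.2936, SE = 0.1198, and exp(0.2152) − 1 = 24.0%. The plan states 24%.
- All ten precision estimates in Protocol Table 6 reproduce on n − 1 df. At n = 6 for AUC, n − 1 df gives the stated 26%, while n − 2 df gives 28%. The sizing therefore followed the protocol model without period.
- The 90% CIs printed beside these figures are wider, because they equal (1 − p, 1/(1 − p)) with p the precision; for example, 1/0.84 = 1.19. That is a separate matter and does not affect this point.

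**2. Fixed order.** Code fed and period as 0/1, with intercept a, food effect f and period effect g.

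- Period 1 (all fasted): mean = a
- Period 2 (all fed): mean = a + f + g

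Two means identify a and the sum f + g, never f alone. The columns for fed, period and fed×period are identical. [1, fed, period] has rank 2 of 3, and adding the interaction gives rank 2 of 4. The fed contrast is outside the row space at n = 10, 12 and 14. Dropouts do not change this (rank still 2), and CVw plays no part.

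**3. Two sequences, 1:1.** The mean Period 2 − Period 1 difference is g + f for fasted-first and g − f for fed-first. Half the difference between them is f, with SE again s·√(2/n), on n − 2 df. Rank is 3 of 3, and 4 of 4 with the interaction. With seq = 1 for fed-first, seq = fed + period − 2·fed×period. Once the main effects are in the model, the interaction is therefore the sequence effect.

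**4. Cost of the period term with two sequences (n = 12)**

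| CVw | Without period (df 11) | With period (df 10) |
|---|---|---|
| 20% | 0.865–1.156 | 0.864–1.158 |
| 30% | 0.806–1.240 | 0.805–1.243 |

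**5. Fixed order with period dropped.** The estimate is now of f + g, so a period ratio p multiplies the reported ratio by p. With no true food effect, the chance that the nominal 90% CI covers 1 follows from a noncentral t with 11 df and noncentrality ln(p)/SE. For p = 0.90 at CVw 20%, the noncentrality is −0.1054/0.0808 = −1.30.

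| Assumed p | CVw 20% | CVw 30% |
|---|---|---|
| 0.90 | 66% | 79% |
| 0.95 | 84% | 87% |
| 1.05 | 85% | 88% |
| 1.10 | 70% | 81% |

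A simulation of 200,000 runs at p = 0.90 and CVw 20% gave 66.2%, against 66.1% from the formula.

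**The case against.** The randomised reading has real support. Besides Protocol 7.3.1 and the 1:1 ratio, the documents call Cohort 3 a crossover, Protocol 5.2 assigns replacements to the same sequence as the person replaced, and allocations sit in a separate randomisation schedule. A period term is also what one expects with a randomised order. On that reading the model is estimable, and only the period labels are wrong. This stands as a condition on the finding but does not remove the conflict. The fixed-order labels recur in both documents, and the word crossover does not settle the matter, since Part A also applies it to the ascending doses of Cohorts 1 and 2.

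The failure would also be visible. Aliased columns give no estimate rather than a wrong one, a dry run precedes database lock, and the protocol model is a ready substitute. SAP 8.2.5.1 also allows adjustments after its model checks. True, but that clause names no model and would leave the choice until data are in hand. The listed covariance fallbacks do not alter the rank of the fixed effects.

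The food effect is a secondary estimate with no hypothesis test, and no participant, dose or primary endpoint is affected. That limits the consequence.

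The coverage figures describe a different model (period dropped) under assumed period ratios. Carry-over is unlikely, with at least 10 days between doses and a predicted half-life of about 1.3 hours. Both points are fair, but carry-over is not the only source of a period effect.

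Finally, the protocol leaves statistical detail to the analysis plan, so adding period is arguably delegated. SAP 2.1 nevertheless records another minor change, and this one belongs beside it.

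**Conclusion.** The concern holds. The two accounts of the order cannot both be right for Cohort 3. If the fixed order is the one run, the fed–fasted contrast in SAP 8.2.5.1 and Table 4.7 is not estimable; this is exact algebra that needs no assumption about variability or sample size. If two sequences are randomised 1:1, the main-effects model is sound and period costs about 0.002 on the upper 90% limit at CVw 20% and n = 12, but about half the participants are fed in Period 1, against the labels in both documents. The coverage loss for a fixed order without a period term (66% to 88% across the four assumed period ratios and both CVw values, against a nominal 90%) depends on assumed period effects that the documents neither give nor rule out. The conflict should be resolved before the final model is run.

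**What to change.** Reconcile Protocol 5.6.2, SAP 3.1 and 3.1.1.3 and the Cohort 3 row of SAP Figure 1 with Protocol 7.3.1 and SAP 2.3, so that one sequence scheme is stated. Then match the model to it. This review takes no position on which order is clinically right.

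- **If two randomised sequences:** write them out and correct the period labels and the figure. Keep fed status, period and random subject. Drop the fed-by-period interaction conditional on a significance test, since it is the sequence effect. Record the added period term in SAP 2.1.
- **If fixed order:** remove period and the interaction from SAP 8.2.5.1 and period from the Table 4.7 footnote, and use the protocol model (fed/fasted plus subject). State, for both the interim ratio summary and the final estimate, that they assume no period effect.

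The cost is sequence wording in both documents, one model line, one table footnote and, where period is kept, one line in SAP 2.1. No extra participants or procedures are needed.
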